## 1. INTRODUCTION

### 1.1. Background and rationale for the study

Maternal immunization aims to prevent diseases in neonates and infants via transplacental antibody transfer from the mother to the fetus following vaccination of the pregnant woman. Several marketed vaccines are already recommended for and routinely administered to pregnant women, including influenza, tetanus and Tdap vaccines [CDC, 2013a, CDC, 2013b]. There are also a number of maternal vaccines in development that aim to protect neonates and infants from pathogens in addition to, respiratory syncytial virus (RSV). GlaxoSmithKline (GSK) is developing an investigational vaccine for use in pregnant women, against RSV disease. Of note this vaccine is developed solely for immunization in pregnancy.

Maternal immunization is implemented worldwide and has the potential to make a major contribution to reducing RSV lower respiratory tract illnesses (LRTI) and the burden of other diseases in infants globally. Therefore, it is imperative that clinical trials are conducted across different countries in different settings. GSK is proactively addressing potential challenges of conducting clinical trials in pregnant women in low- and middle income countries (LMIC).

Before conducting clinical trials it is important to understand the frequency of pregnancy outcomes and the maternal and neonatal events of interest (i.e. clinically significant events that may be considered adverse events if they occur after vaccination) in each setting where clinical trials may be conducted for better interpretation of safety data. Also, to ensure safety of the participating women, and to characterize the safety profile of the product, adverse events (AEs) in pregnancy should be appropriately detected and managed. This study addresses gaps in understanding of anticipated rates of pregnancy outcomes as well as events of interest in pregnant women and neonates. Furthermore, this study will be conducted at potential sites for future maternal immunization trials and will help assure the capacity of sites to detect and manage clinically significant events of interest in pregnant women and their neonates.

Secondarily, the study will establish surveillance mechanisms for RSV associated illnesses in the neonate/infant (through the first 12 months of life). Whilst there is good documentation of the global burden of RSV disease, incidence of RSV-LRTI according to the World Health Organization (WHO) 2015 case definitions [Modjarrad, 2016] is limited in the literature, particularly in many LMIC settings. Hence, this study will also estimate the incidence of infant RSV-LRTI using WHO case definitions across geographically distinct locations to support incidence rate assumptions for planning of future efficacy trials.

To achieve these goals, GSK will be guided by the WHO recommendations on antenatal care for a positive pregnancy experience [WHO, 2016] and the Global Alignment of Immunization Safety Assessment in pregnancy (GAIA) case definitions [Bonhoeffer, 2016; Bauwens, 2016; Kochhar, 2017]. Standardization of surveillance methodology and case definitions (applicable to maternal immunization AEs) may support comparison of data across different countries [Jones, 2016].

**CONFIDENTIAL**207636 (EPI-RSV-008 BOD)  
Protocol Amendment 4 Final**1.2. Rationale for the study population**

The intention of this epidemiological study is to obtain an estimate of the background rate of adverse pregnancy outcomes and events that may be seen in future vaccine trial populations and, separately, to assess whether sites are suitable for Phase II/III vaccine trials. The study aims to enroll healthy women with normal uncomplicated pregnancies so that event rates for pregnancy and neonatal events of interest are applicable to the intended population for future vaccine trials. Regardless of enrollment location, healthy pregnant women aged 18 to 45 years with normal, uncomplicated, singleton pregnancies, who have had a level 2 (fetal morphology) ultrasound without any significant findings will be eligible for possible study participation. Inclusion / exclusion criteria have been structured in a way that resembles those of Phase II/III criteria to ensure good comparability between the current study population and that of anticipated future vaccine trials.

Pregnant women  $24^{0/7}$  up to and including  $27^{6/7}$  weeks of gestation will be enrolled, to ensure that they are followed as of the time of potential vaccination in a clinical trial.

Women who do not meet the enrollment criteria will be referred for appropriate local standard of care.

**1.3. Rationale for the surveillance of pregnancy related events of interest**

There are particular challenges in conducting clinical trials in pregnant women, among them limited data on background rates of pregnancy outcomes as well as what may be observed in clinical trials as maternal and neonatal adverse events. A large number of countries aim to strengthen their ability to provide comprehensive antenatal care for all and to enable a positive pregnancy experience. The WHO 2016 recommendations on antenatal care for a positive pregnancy experience [WHO, 2016] give guidance on the frequency of clinic visits, examination procedures and screening tests.

To achieve these goals, GSK will be guided by the WHO recommendations on antenatal care for a positive pregnancy experience [WHO, 2016] and the Global Alignment of Immunization Safety Assessment in pregnancy (GAIA) case definitions [Bonhoeffer, 2016; Bauwens, 2016; Kochhar, 2017]. Standardization of surveillance methodology and case definitions (applicable to maternal immunization AEs) may support comparison of data across different countries [Jones, 2016].

The number and timing of study visits was informed by WHO recommendations on antenatal care [WHO, 2016]. However, local standards of care differ from country-to-country. Women should follow the local standard of care. Study data will be collected, in part, from records of the data obtained during the locally recommended antenatal care visits.

In this study, best efforts will be made to work with local healthcare providers to collect the key data on maternal, fetal, neonatal and infant health from routine health records to avoid duplication and an undue burden on the trial subjects.

**CONFIDENTIAL**207636 (EPI-RSV-008 BOD)  
Protocol Amendment 4 Final**1.4. Rationale for the use of Global Alignment of Immunization safety Assessment in pregnancy (GAIA) case definitions**

GAIA, a Brighton collaboration project, aims to develop standardized case definitions and criteria for diagnostic certainty of maternal outcomes and events of interest and neonatal events of interest in the context of immunization trials [Bauwens, 2016; Bonhoeffer, 2016; Kochhar, 2017].

GAIA was established in response to a WHO request to work on a globally aligned approach to monitor safety of maternal immunization clinical trials. The application of these case definitions (APPENDIX D) aims to improve the quality of data generated and to support safety assessment. The goal is to pilot these case definitions prior to the initiation of large maternal immunization trials. To achieve this, the level of diagnostic certainty (APPENDIX D) will be collected for all of the events of interest for which GAIA criteria have been developed.

**1.5. Rationale for the active and passive surveillance for RSV associated respiratory tract illnesses (RTI) with suspicion of difficulty in breathing/wheezing or with parental concern in neonates/ infants**

RSV infects 50-70% of infants in their first year of life, and practically all children have experienced RSV infection and / or illness by their third birthday [Hall, 2009]. In industrialized countries, approximately 2% of infants under one year of age are hospitalized as a consequence of RSV-induced lower respiratory tract illnesses (LRTI) each year. Infants younger than six months have the highest risk of developing severe RSV-induced LRTI. Approximately half of all pediatric LRTI occur in the first six months of life, and LRTI is the leading cause of hospitalization in this age group [Boyce, 2000; Deshpande, 2003; Hall, 2009; Holman, 2004; Iwane, 2004; Nair, 2010; Vicente, 2003].

The implementation of surveillance will also assist in establishing robust infrastructure and processes for RSV-LRTI and RSV hospitalization detection in future vaccine trials.

CONFIDENTIAL

207636 (EPI-RSV-008 BOD)  
Protocol Amendment 4 Final

## 2. BENEFIT: RISK ASSESSMENT

The following section outlines the risk assessment and mitigation strategy for this study protocol:

### 2.1. Risk Assessment

Important Potential/Identified Risk	Data/Rationale for Risk	Mitigation Strategy
Study Procedures		
Blood sample collection- While giving blood the subject may feel faint, or locally experience mild pain, bruising, irritation or redness.	Spontaneous data	Sample collection will only be performed by appropriately trained study personnel. All subjects will remain under observation, post venipuncture, through completion of the applicable study visit. Subjects will be notified of this risk in the informed consent form.
Nasal swab collection from infant subjects may cause discomfort	Spontaneous data	Sample collection will only be performed by appropriately trained personnel. Subjects' parent(s)/LAR(s) will be notified of this risk in the informed consent form.

### 2.2. Benefit Assessment

Study participation may have limited or no benefit for the study subjects themselves.

Study procedures aim to ensure surveillance for maternal outcomes and events of interest and neonatal events of interest. The attention to surveillance may enhance the ability to detect these safety events and to refer subjects for management according to local standard of care. The protocol also includes procedures that may enhance surveillance for RSV, and possibly other lower respiratory tract illnesses, in neonates and infants. Thus, the procedures described in this protocol may enhance the ability to detect these events or illnesses and to refer subjects for management according to local standard of care.

Data collected during the study may enhance understanding of the frequency of maternal events of interest in women with low risk pregnancies, neonatal events of interest, and RSV-associated lower respiratory tract illnesses in neonates and infants.

Surveillance methods explored and data collected during this study may inform future care and prevention efforts and will be used to design robust monitoring systems for future clinical trials of maternal immunization.

### 2.3. Overall Benefit:Risk Conclusion (Amended 29-MAY-2020)

*This is an epidemiologic study that describes the prevalence of pregnancy outcomes and maternal/neonatal events of interest. The study does not include the administration of any investigational vaccine. It is not expected that the participation of pregnant women and their babies in the study would create any further risk to study participants. The study includes the establishment of a surveillance system for lower respiratory tract infections (LRTI) which may facilitate detection of respiratory tract infections, including COVID-19 cases, that might be diagnosed in children enrolled in the study.*

**CONFIDENTIAL**207636 (EPI-RSV-008 BOD)  
Protocol Amendment 4 Final

Potential risks to subjects participating in this study are limited to those associated with the collection of biological specimens. Taking into account the measures to minimize these potential risks for subjects participating in this study, the potential or identified risks are justified by the potential benefits of enhanced surveillance for the subjects, and by the knowledge gained about the frequency of events of interest.

### **3. OBJECTIVES**

#### **3.1. Primary objectives**

*In healthy pregnant women with uncomplicated pregnancies:*

- To determine the frequencies of pregnancy outcomes.
- To determine the frequencies of pregnancy related events of interest from enrollment (Visit 1) through 42 days after delivery (Visit 6). (Although pregnancy related events of interest occur within the first 42 days after delivery they may only be detected later, and are to be reported throughout the study.)

*In all neonates live-born to women enrolled in the study:*

- To determine the frequencies of neonatal events of interest.

Neonatal events of interest occur within the first 28 days after birth, but may only be detected later and are to be reported throughout the study.

**Refer to Section 11.1.1 for the definition of the primary endpoints.**

#### **3.2. Secondary objectives**

*In healthy pregnant women with uncomplicated pregnancies at enrollment:*

- To determine frequencies of pregnancy related events of interest according to GAIA levels of diagnostic certainty (where these are specified) ([APPENDIX D](#)) from enrollment (Visit 1) through 42 days after delivery (Visit 6). (Although pregnancy related events of interest occur within the first 42 days after delivery they may only be detected later, and are to be reported throughout the study.)
- To describe the distribution of RSV-A antibody titers in maternal blood at delivery.

*In all neonates live-born to women enrolled in the study:*

- To determine frequencies of neonatal events of interest according to GAIA levels of diagnostic certainty (where these are specified). ([APPENDIX D](#)). Neonatal events of interest occur within the first 28 days after birth, but may only be detected later and are to be reported throughout the study.
- To describe the distribution of RSV-A antibody titers in cord blood at delivery.

**CONFIDENTIAL**207636 (EPI-RSV-008 BOD)  
Protocol Amendment 4 Final

*In all neonates/infants live-born to women enrolled in the study, from birth through 1 year of age:*

- To determine the incidence of all, of severe, and of very severe RSV-lower respiratory tract illnesses (LRTIs).
- To determine the incidence of RSV hospitalization.
- **Refer to Section 11.1.2 for the definition of the secondary endpoints.**

Refer to the [GLOSSARY OF TERMS](#) for the definition of enrollment.

### **3.3. Tertiary objectives (Amended 29-MAY--2020)**

- To describe co-infections of RSV-LRTI with other respiratory viruses in infants.
- To estimate the association of RSV-LRTI in neonates/infants and the level of RSV neutralizing antibodies in cord blood.
- ***To determine the incidence of LRTIs/Severe LRTIs (using alternative case definitions)***
- To determine risk factors for pregnancy-related and neonatal events of interest.
- If deemed necessary, to further characterize the immune responses to RSV and other infections in maternal subjects and infants (based on maternal serum and cord blood).

[figure not shown]
**Refer to Section 11.1.3 for the definition of the tertiary endpoints.**

CONFIDENTIAL

207636 (EPI-RSV-008 BOD)  
Protocol Amendment 4 Final

## 4. STUDY DESIGN OVERVIEW (AMENDED 29-MAY-2020)

Figure 1 Study design (Amended 29-MAY-2020)

D = day; M = month; V = visit; W = week; Y = year. NB = newborn; GA = Gestational age; BS = blood sample; US = urine sample for dipstick testing; IMM = immune response; HB = hematology/biochemistry; RBC = red blood cell(s); WBC = white blood cell(s); RSV = respiratory syncytial virus; RTI = respiratory tract illness; LRTI = lower respiratory tract illness;

Refer to Section 11.11 for additional information about the analyses indicated above.

If delivery occurs prematurely, skip to Visit 5 ("at delivery").

At Delivery, RSV-A antibody titers for all women

At V3, only hemoglobin testing.

Allowed interval for blood sample collection begins with start of labor (e.g. when the mother arrives at the hospital to deliver and an intravenous line is inserted) and ends 72 hours after delivery.

RSV-A antibodies in cord blood

Neonatal events of interest occur (by definition) between 0 and 28 days after birth. They will be reported once site staff become aware of them (whether this occurs during the first 28 days after birth, or at a later time).

**NOTE: Covid-19 cases identified within the surveillance framework of the study in maternal and infant subjects will also be recorded.**

Protocol waivers or exemptions are not allowed unless necessary for the management of immediate safety concerns. Therefore, adherence to the study design requirements, including those specified in the outline of study procedures (Section 8.3), are essential and required for study conduct.

**CONFIDENTIAL**207636 (EPI-RSV-008 BOD)  
Protocol Amendment 4 Final

- Type of design: Prospective, epidemiological, interventional (without administration of medicinal products as described in a research protocol), multi-country, cohort study.
- Study population: The study will be conducted in multiple countries, in pregnant women and their infants.
- Type of study: self-contained.
- Data collection: Electronic Case Report Form (eCRF).

**Table 1 Sampling schedule for maternal subjects**

Sample	Parameter(s) evaluated	Visit				
		1	2	3	4	Delivery
Maternal Blood	Hematology/ biochemistry 		x		x 	
	Antibody titer (RSV-A)					≤ 72 hours after delivery 
Cord Blood	Antibody titer (RSV-A)					x
Urine	Protein, glucose, RBC, WBC 	x	x	x	x	

 To be performed preferentially by local healthcare providers, as per local practice. To be performed by the investigator/study staff ONLY if not done by the local healthcare provider within 2 weeks before the study visit.

 The investigator/site staff will perform a urine dipstick test using supplies provided by GSK.

 Hemoglobin only

 If results are abnormal, subjects will be referred per local standard of care.

 This sample may be collected from start of labor (e.g. when the mother arrives at the hospital to deliver and an intravenous line is inserted) through 72 hours after delivery.

- Sampling schedule for **neonates/infants**: Surveillance for RSV LRTI will be conducted in infants through the 12 month study period. During this 1-year post-birth surveillance period, for each RTI with suspicion of difficulty in breathing, or wheezing, or with parental concern, a nasal swab will be collected at a visit to assess potential RSV associated RTIs/LRTIs.
- Primary Completion Date (PCD): 42 days post-delivery/birth (i.e. Visit 6 for maternal subjects and Visit 2-NB for infant subjects) or last visit of Epoch 002.
- End of Study (EoS): Last testing results released of samples collected up to Visit 4-NB (assays related to primary and secondary endpoints).
- Duration of the study: Approximately 4.5 to 6 months for maternal subjects; approximately 1 year for infant subjects.
  - Epoch 001: Screening
  - Epoch 002: Primary starting at Visit 1 and ending 42 days post-delivery/birth (Visit 6 for maternal subjects and Visit 2-NB for infant subjects).\*
  - Epoch 003: Follow-up of infants starting 43 days post-delivery/birth and ending at Visit 4-NB (1 year post-birth).

\*Any safety and disease surveillance data collected after Visit 2-NB will be collected in Epoch 003.

**CONFIDENTIAL**207636 (EPI-RSV-008 BOD)  
Protocol Amendment 4 Final**Table 2 Study groups and epochs foreseen in the study**

Study Groups	Number of subjects enrolled	Age (Min/Max)	Epochs		
			Epoch 001	Epoch 002	Epoch 003
Maternal subjects	Up to ~ 2300	18 years - 45 years	x	x	
Infants	Up to ~ 2300	NA		x	x

Approximately 200 to 300 per country. To achieve the enrollment targets noted above, the number of pregnant women SCREENED in each country may exceed the country-specific enrolment goal.

- Surveillance for pregnancy outcomes and pregnancy-related events of interest(Section 8.5.8) that occur from Visit 1 up to 42 days after delivery (Visit 6).
- Surveillance for neonatal events of interest(Section 8.6.3) that occur from birth up to 28 days of age.
- Surveillance for RSV LRTI and RSV hospitalization (refer to Section 8.6.8) in infants, from birth up to 1 year of age.

## 5. CASE DEFINITIONS

### 5.1. Pregnancy related events of interest

Pregnancy related events of interest are briefly defined in the [GLOSSARY OF TERMS](#), listed in Section 11.1 and described in detail in [APPENDIX D](#).

### 5.2. Neonatal events of interest

Neonatal events of interest are briefly defined in the [GLOSSARY OF TERMS](#), listed in Section 11.1 and described in detail in [APPENDIX D](#).

### 5.3. Respiratory tract illness (RTI) / Lower respiratory tract illness (LRTI)

During data analysis, cases of respiratory tract illness (RTI) identified from birth up to 1 year of age will be classified according to the case definitions in [Table 3](#).

### 5.4. RSV infection (Amended 29-MAY-2020)

Nasal swabs will be analyzed by the sponsor for the presence of RSV A/B. A positive test result constitutes a case of RSV infection. Refer to Section 8.6.7.3.

**CONFIDENTIAL**207636 (EPI-RSV-008 BOD)  
Protocol Amendment 4 Final**Table 3 RTI/LRTI case definitions for data analysis**

RSV-RTI	Runny nose, OR Blocked nose, OR Cough AND Confirmed RSV infection 
RSV-LRTI	History of cough OR difficulty in breathing  AND SpO 2 < 95%  , OR RR increase  AND Confirmed RSV infection 
RSV-severe LRTI	Meeting the case definition of RSV-LRTI AND SpO 2 < 93%, OR lower chest wall in-drawing
RSV-very severe LRTI	Meeting the case definition of RSV-LRTI AND SpO 2 < 90%, OR inability to feed OR failure to respond / unconscious
RSV hospitalization	Confirmed RSV infection  AND Hospitalized for acute medical condition 
All-cause RTI	Runny nose, OR Blocked nose, OR Cough
All-cause LRTI	History of cough OR difficulty in breathing  AND SpO 2 < 95%  , OR RR increase 

Definitions based on [Modjarrad, 2016]

**RTI** = respiratory tract illness; **LRTI** = lower respiratory tract illness; **RR** = respiratory rate; **SpO2** = blood oxygen saturation by pulse oximetry.

 Based on history reported by parents/LARs and includes difficulty in breathing (e.g. showing signs of wheezing or stridor, tachypnoea, flaring [of nostrils], chest in-drawing, apnoea).

 For blood oxygen saturation (SpO2), the lowest value monitored will be used. In high altitudes (>2500m), SpO2 <92% for LRTI, <90% for severe LRTI, <87% for very severe LRTI.

 RR increase defined as:

- > 60/minute (< 2 months of age)
- > 50/minute (2 to < 12 months of age)
- > 40/minute (12 to 24 months of age)

 RSV infection confirmed on nasal swab positive for RSV A or B by quantitative reverse transcription polymerase chain reaction (qRT-PCR).

 RSV sampling and testing is described in Sections 8.6.7, 8.6.8 and 8.6.9.

 Hospitalization is defined as admission for observation or treatment based on the judgement of a health care provider

**CONFIDENTIAL**207636 (EPI-RSV-008 BOD)  
Protocol Amendment 4 Final**Table 4 Alternative LRTI / Severe LRTI Case Definitions (Amended 29-MAY-2020)**

		Documented physical examination (PE) findings indicating lower respiratory tract involvement (at least one symptom)	Objective measures of clinical severity (at least one symptom)
LRTI	Confirmed RSV infection	Rhonchi Rales Crackles Wheeze	Increased respiratory rate (bpm) $\geq 60$ for < 2 mo $\geq 50$ for 2-6 mo  Hypoxemia: SpO2 <95% at <math>\leq 1800</math> meters SpO2 <92% at > 1800 meters  New onset apnea Nasal flaring Retractions Grunting
Severe LRTI	Confirmed RSV infection	Rhonchi Rales Crackles Wheeze	Hypoxemia  SpO2 <93% at <math>\leq 1800</math> meters SpO2 <90% at > 1800 meters  Acute hypoxic or ventilatory failure Dehydration due to respiratory distress requiring IV hydration Failure to respond or unconscious

Term not listed in the eCRF page in this study.Intercostal recession or chest wall indrawing are considered synonymous with and will be used as alternatives to the term "retractions," which is not listed in the eCRF page for this study.Acute hypoxic or ventilatory failure is not listed in the eCRF page for this study. Instead, the presence of either respiratory support excluding mechanical ventilation OR requirement for mechanical ventilation or both will be used.Dehydration due to respiratory distress requiring IV hydration is not listed in the eCRF page for this study. Skin turgor > 2 seconds or administration of IV fluid therapy will be used instead.

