**11.1.3. Tertiary endpoints (Amended 29-MAY-2020)**

- Co-infections of RSV-LRTI with other respiratory viruses in infants, confirmed by PCR of nasal swabs in infants from birth up to 1 year of age:
  - Influenza A virus (Flu A)
  - Influenza B virus (Flu B)
  - Human Influenza A virus subtype H1 (Flu A-H1)
  - Human Influenza A virus subtype H3 (Flu A-H3)
  - Human Influenza A virus subtype H1pdm09 (Flu A-H1pdm09)
  - Human adenovirus (AdV)
  - Human metapneumovirus (MPV)
  - Human enterovirus (HEV)
  - Human parainfluenza virus 1 (PIV1)
  - Human parainfluenza virus 2 (PIV2)
  - Human parainfluenza virus 3 (PIV3)
  - Human parainfluenza virus 4 (PIV4)
  - Human bocavirus 1/2/3/4 (HBoV)
  - Human rhinovirus A/B/C (HRV)
  - Human coronavirus 229E (229E)
  - Human coronavirus NL63 (NL63)
  - Human coronavirus OC43 (OC43)

**CONFIDENTIAL**207636 (EPI-RSV-008 BOD)  
Protocol Amendment 4 Final

- Potential risk factors for pregnancy related and neonatal events of interest.
- Any further exploratory characterization of immune responses to RSV and/or other respiratory tract infections or infections of relevance to pregnant women and their newborns (based on maternal serum and cord blood) (*For example, levels of RSV-B neutralizing antibodies.*)
- *Episode(s) of RSV-LRTI/severe LRTI based on alternative case definitions, from birth up to 1 year of age.*

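### Table 4's alternative Severe LRTI row is not nested in its LRTI row, and footnote 4 lets IV fluids given for any reason make an infant with a chest finding 'severe'

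*Protocol*

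**What the plan says.** Section 5.4 gives two sets of case definitions. In Table 3, both the severe and the very severe rows open with "Meeting the case definition of RSV-LRTI AND", so each is a subset of RSV-LRTI by construction.

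Table 4, added in the 29 May 2020 amendment, gives alternative definitions of LRTI and Severe LRTI. Each row needs three things: confirmed RSV, at least one examination finding of lower-tract involvement (rhonchi, rales, crackles or wheeze), and at least one item from that row's own severity list. The Severe row has no clause requiring the LRTI row.

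Two items in the Severe list are replaced by proxies. Footnote 4 says "Dehydration due to respiratory distress requiring IV hydration is not listed in the eCRF page for this study", and then "Skin turgor > 2 seconds or administration of IV fluid therapy will be used instead". Footnote 3 handles acute hypoxic or ventilatory failure in the same way: "the presence of either respiratory support excluding mechanical ventilation OR requirement for mechanical ventilation or both will be used".

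The endpoint in Section 11.1.3 is "Episode(s) of RSV-LRTI/severe LRTI based on alternative case definitions, from birth up to 1 year of age". Section 11.8 places the incidence under these definitions among the tertiary analyses done by country, region or other grouping.

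**The concern.** The replaced criterion has three parts: a condition (dehydration), a cause (respiratory distress) and a treatment need (IV hydration). The proxy accepts either a skin sign or a treatment. Neither carries the cause, and fluids alone do not carry the condition either. The column is meant to hold objective measures of severity, but giving fluids is a treatment decision.

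Because the Severe row does not refer back to the LRTI row, such a case need show none of the respiratory signs that define LRTI. Two things follow. A severe grade that is not a grade of the illness makes the paired LRTI and Severe LRTI incidences hard to read together. And where care follows local standards, as Sections 8.2 and 8.6.5.2 say it does, a country difference in alternative Severe LRTI can be a difference in how readily infants receive fluids.

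**Working it through.** No sample size or event rate enters, so the check is logical. All inputs come from Tables 3 and 4 and their footnotes.

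**The rules, with RSV confirmed**

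- Chest finding: any of rhonchi, rales, crackles, wheeze. Footnote 1 says the first two are not on the eCRF, so in practice this means crackles or wheeze.
- LRTI = chest finding AND any of six items: raised respiratory rate, SpO2 < 95%, apnea, flaring, retractions, grunting.
- Severe = chest finding AND any of five items: SpO2 < 93%, respiratory support or ventilation (footnote 3), skin turgor > 2 s (footnote 4), IV fluids (footnote 4), unresponsive.
- The thresholds shown are for altitudes up to 1800 m. Those for higher sites nest in the same way.

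**Is Severe a subset of LRTI?** Treat the 12 items (1 + 6 + 5) as yes/no.

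1. All combinations: 2^12 = 4096. Remove those with SpO2 < 93% but not < 95%, which are impossible: 2^10 = 1024. Remaining: 3072.
2. With a chest finding: 3072 / 2 = 1536. Of these, 2^6 = 64 have no Severe item. Severe: 1536 − 64 = 1472.
3. Severe with none of the six LRTI items: SpO2 < 93% is then excluded, leaving four free items of which at least one is present: 2^4 − 1 = 15.
4. Severe without a chest finding: 0.

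So 15 combinations are Severe but not LRTI. IV fluids are present in 2^3 = 8 of them and are the only Severe item in 1. Only the proxies of footnotes 3 and 4 are at work in 2^3 − 1 = 7.

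**Example 1.** An RSV-positive infant aged 4 months has wheeze, respiratory rate 44/min, SpO2 97%, no apnea, flaring, retractions or grunting, and IV fluids for vomiting.

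| Rule | Test | Result |
|---|---|---|
| Table 4 LRTI | 44 is below 50; 97% is not below 95%; no other sign | Not met |
| Table 4 Severe | Chest finding and IV fluids | Met |
| Table 3 RSV-LRTI | Neither SpO2 < 95% nor rate > 50 | Not met, so cannot be severe |

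**Example 2.** A 9-month-old has wheeze, rate 65/min and SpO2 96% on respiratory support, with no other sign. Table 4's respiratory-rate item stops at 6 months, although the endpoint runs to 1 year. This infant is therefore Severe through footnote 3 but not LRTI. Nesting alone would make the infant neither. Table 3 already has a cut-off for 2 to < 12 months (> 50/min). With an equivalent item in Table 4 the infant is LRTI and stays Severe.

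**What nesting does and does not cure.** Requiring the LRTI row takes the 15 to 0. It leaves combinations in which an LRTI case is Severe through IV fluids alone: a chest finding, IV fluids as the only Severe item, and at least one of the six LRTI items, 2^6 − 1 = 63. That is why separate reporting is needed as well.

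**The case against.** The strongest reply is that the problem is narrow and the protocol is open about it. Table 4 serves one tertiary objective. It says plainly which terms the eCRF lacks and what replaces them, and a sensitive 'or' proxy is a legitimate choice. The eCRF is not shown; if IV fluids are recorded on the LRTI assessment page as treatment of that episode, part of the link to respiratory illness may exist in the data. This stands as a limit on size. It does not remove the defect, because footnote 4 sets no such condition and the missing nesting does not depend on the eCRF.

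Four stronger readings are tempting and not supported:

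- **That mild RSV illness in general becomes severe through fluids.** The Severe row still needs confirmed RSV and a documented chest finding. No combination without a chest finding qualifies.
- **That planning of future efficacy trials is compromised.** Section 1.1 ties incidence assumptions for those trials to the WHO definitions, which are the basis of Table 3, and the possible interim look at case-definition performance in Section 11.11.1 cites Table 3 only.
- **That severe incidence is inflated by a stated factor.** If 10 of 100 infants with a chest finding were severe by other criteria and 5–20% of the other 90 received fluids, the factor would be (10 + 4.5)/10 = 1.45 to (10 + 18)/10 = 2.8. Both rates are assumptions with no source in the protocol.
- **That footnote 4 should read 'and'.** Turgor plus fluids still has no link to respiratory distress: a dehydrated, vomiting infant would qualify. True cases would be lost where turgor was not recorded, which is likely when a missed visit is completed from medical records (Section 8.6.7.4).

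**Conclusion.** The point holds for RSV-positive infants with a chest finding. As written, Table 4 can classify such an infant as Severe LRTI but not LRTI, and IV fluids for any reason are enough to do it. Fifteen of 1472 qualifying combinations show the non-nesting. They are logical possibilities and carry no weight as frequencies. The size in cases or incidence cannot be derived from the protocol.

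The consequence is confined to the tertiary endpoint on alternative definitions and matters most for its country or regional comparisons. The primary endpoints and the Table 3 secondary endpoints are unaffected. The conclusion rests on reading the Severe row and footnotes 3 and 4 literally, with no condition implied beyond their text. The correction is worth making because it concerns a rule the protocol itself fixes and costs little.

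**What to change.** 1. In Table 4, open the Severe LRTI row with a clause requiring the alternative LRTI definition, as Table 3 does for its severe rows.
2. Extend the respiratory-rate item in the LRTI row beyond 6 months, so that nesting does not drop older infants. Table 3 already has a band for 2 to < 12 months. State the inequality, since Table 4 uses ≥ 50 and Table 3 uses > 50.
3. Keep the 'or' in footnote 4. Report alternative Severe LRTI incidence with and without cases whose only qualifying Severe item is IV fluid therapy, and do the same for the respiratory-support proxy of footnote 3.

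These are changes to derivation and reporting. The footnotes imply that the items are already collected, so no new data should be needed. The cost is one extra table and the loss from the main figure of a few infants who are severe without any LRTI-row sign. That group is mostly proxy-only cases, but it could include an unresponsive infant with only a chest finding, or one whose SpO2 was measured on support, because Section 8.6.7.2 asks for room air only where feasible. The number dropped should be shown beside the table.
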